1 PROTOCOL SUMMARY

1.1 SYNOPSIS

Title:	Sleep GOALS (Goal-focused Online Access to Lifestyle Support)
Study Description:	This study will use a single-blind, parallel-arm, randomized controlled trial design. Participants will be randomized at a 1:1 ratio to the Sleep GOALS intervention or education control group. We will measure indicators of study feasibility and acceptability to identify and refine factors related to the conduct of the planned larger trial and intervention content and estimate the change in secondary outcomes. See Schema and Schedule of Activities, Sections 1.2 and 1.3 , respectively.
Objectives:	Primary Objective: To determine the feasibility and acceptability of Sleep GOALS Secondary Objectives: To determine the preliminary efficacy of Sleep GOALS
Endpoints:	Primary Endpoint: The intervention's feasibility (i.e., recruitment, enrollment, attrition rates, intervention engagement) and acceptability (i.e., participant ratings of the intervention delivery, curricula, action plans, intervention platform, and coaching) Secondary Endpoint: Weight loss and retention of pregnancy and postpartum weight gain
Study Population:	40 individuals from Allegheny County who are between 3±1 and 6±1 postpartum, has a body mass index ≥ 25 kg/m ² , self-report less than 150 minutes of moderate-to-vigorous intensity physical activity (e.g., brisk walk) per week, self-report at least one sleep disturbance, and has Internet access.
Phase:	N/A
Description of Sites/Facilities	Baseline and post-intervention assessments will occur at the Perinatal Health Behavior (PHB) Lab on the University of Pittsburgh's campus, [name]. Post-intervention semi-structured interviews will take place in the PHB lab or Zoom, at the participant's preference. Baseline assessments will occur prior to randomization (Week 0), and post-intervention assessments will occur immediately following completion of the 16-week intervention period (Week 16)
Enrolling Participants:	

Description of Study Intervention:	16-week online intervention that includes 1) informational videos that provide strategies to improve sleep, diet, and physical activity to achieve weight loss, 2) a lifestyle coach, 3) a commercial activity tracker (e.g., Fitbit Charge 5) to monitor sleep and physical activity, and 4) wireless scale (e.g., Aria) to monitor weight.

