Analysis Plan: The primary study objective is to assess the feasibility and acceptability of Sleep GOALS. We will assess the feasibility of the intervention by estimating rates of recruitment, retention, and engagement (i.e., weekly logins; modules completed; daily self-monitoring of diet, physical activity, and sleep; weekly monitoring of weight using point estimates (means or sample proportions) and 95% confidence intervals). We will assess acceptability by estimating satisfaction rates on various intervention components (≥ 4 Acceptability and Feasibility Questionnaire). Our benchmarks for feasibility are similar to those used in the original GOALS Lifestyle intervention. We will use a benchmark of 80% for all feasibility and acceptability measures. To assess the intervention's preliminary efficacy, we will calculate point estimates and confidence intervals for change in weight and PWR. We chose these weight measures as our secondary outcomes since they will be the primary outcome in the future R01. However, we will also explore changes in our proposed behavioral mediators, sleep, diet, and physical activity to inform power calculations for a fully powered study.

We will conduct an exploratory analysis to determine how potential covariates (e.g., parity, breastfeeding status, postpartum depression, race/ethnicity, relationship status, and employment status) impact the intervention's feasibility, acceptability, and preliminary efficacy. For example, in some studies, breastfeeding is associated with longer nocturnal sleep²⁻⁴, but shorter nocturnal sleep in other studies.⁵ Collecting data on breastfeeding and other covariates will provide preliminary data on how it impacts the intervention.

Domain	Measure, Method of Assessment	Benchmarks for Success
Feasibility (Primary Outcome)		
Recruitment/Enrollment	Total sample	40 participants in 12 months
	Demographics of sample	$\geq 30\%$ ethnic minority
Retention	Attrition Rates	$\leq 20\%$ loss to follow-up
Engagement	Modules completed	≥ 14 (~80%) modules completed within 16 weeks
	Weekly self-monitoring of diet, sleep, and physical activity weekly	≥ 14 (~80%) weeks, ≥ 1 day of monitoring
	Weekly weigh-ins	≥ 14 (~80%) weeks, ≥ 1 day of weigh-ins
	Total time logged in	
Acceptability (Primary Outcome)		
Acceptability	Acceptability of the intervention delivery; behavior change curricula; action plan; intervention platform	$\geq 80\%$ agree or totally agree with each
Preliminary efficacy (Secondary Outcome)		

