5 STUDY POPULATION

We will enroll 40 primiparous adult individuals between 3 \pm 1 and 6 \pm 1 months postpartum with a body mass index \geq 25 kg/m². We chose this postpartum range because postpartum weight retention during this period is associated with the development of long-term obesity. Additionally, at 3 months postpartum, most infants experience rapid increases in nocturnal sleep; thus, many of our behavioral strategies for improving maternal sleep may be more feasible. Evidence suggests that addressing sleep in infants between 3 and 6 months can prevent longer-lasting sleep problems. Lastly, it is safe for most postpartum individuals to participate in an intervention involving physical activity during this period.

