5.1 INCLUSION CRITERIA

To be eligible to participate in this study, an individual must meet all of the following criteria:

1. Provision of signed and dated informed consent form,
2. Stated willingness to comply with all study procedures and availability for the duration of the study,
3. Primiparous, singleton pregnancy,
4. Between 3 \pm 1 and 6 \pm 1 months postpartum,
5. Has a body mass index $>$ 25 kg/m²,
6. Physically inactive, defined as self-reporting $<$ 150 minutes/week of moderate-to-vigorous intensity physical activity,
7. Endorse $>$ 1 indicator of poor sleep health based on the RU_SATED questionnaire, and
8. Has smartphone and home Internet access

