9.4.2 ANALYSIS OF THE PRIMARY EFFICACY ENDPOINT(S)

The primary endpoints are the feasibility and acceptability of Sleep GOALS. We will assess the feasibility of the intervention by estimating rates of recruitment, retention, and engagement (i.e., weekly logins; modules completed; daily self-monitoring of diet, physical activity, and sleep; weekly monitoring of weight using point estimates (means or sample proportions) and 95% confidence intervals). We will assess acceptability by estimating rates of satisfaction on various components of the intervention (≥ 4 Acceptability and Feasibility Questionnaire). Our benchmarks for feasibility are similar to those used in the original GOALS Lifestyle intervention. We will use a benchmark of 80% for all feasibility and acceptability measures. To assess the intervention's preliminary efficacy, we will calculate point estimates and confidence intervals for change in weight and PWR. We chose these weight measures as our secondary outcomes since they will be the primary outcome in the future R01. However, we will also explore changes in our proposed behavioral mediators, sleep, diet, and physical activity to inform power calculations for a fully powered study.

We will conduct an exploratory analysis to determine how potential covariates (e.g., parity, breastfeeding

status, postpartum depression, race/ethnicity, relationship status, and employment status) impact the intervention's feasibility, acceptability, and preliminary efficacy. For example, in some studies, breastfeeding is associated with longer nocturnal sleep, but shorter nocturnal sleep in other studies. Collecting data on breastfeeding and other covariates will provide preliminary data on how it impacts the intervention.

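### Parity is named as a covariate although eligibility fixes it, so its effect cannot be estimated; time since delivery varies by design and is not named, and adjusting the weight estimates for it could modestly improve precision

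*Combined protocol and SAP*

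**What the plan says.** **Covariates.** Section 9.4.2 proposes to explore "how potential covariates (e.g., parity, breastfeeding" "status, postpartum depression, race/ethnicity, relationship status, and employment status) impact the intervention's feasibility, acceptability, and preliminary efficacy". The Analysis Plan in Section 3 gives the same six: "potential covariates (e.g., parity, breastfeeding status, postpartum depression, race/ethnicity, relationship status, and employment status". Both lists are introduced as examples.

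**Eligibility.** Criterion 3 in Section 5.1 reads "Primiparous, singleton pregnancy", and Section 5 opens with "We will enroll 40 primiparous adult individuals". The synopsis (Section 1.1) does not mention primiparity.

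**Entry window.** The synopsis gives "between 3±1 and 6±1 postpartum" without a unit; Sections 5 and 5.1 supply months. Section 5 justifies the window partly by the rapid lengthening of infant night sleep at about 3 months, which may make the maternal sleep strategies more feasible. Time since delivery or infant age is not in either covariate list or among the Section 8.1 assessments. Section 6.2 names no stratification factor, only blocks of 4.

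**Weight outcomes.** Section 3 defines PWR as measured post-intervention weight minus self-reported pre-pregnancy weight, and says the secondary outcomes will supply estimates of the intervention's effect for the larger trial. Section 9.4.1 specifies descriptive statistics, Section 9.4.2 point estimates and confidence intervals, and Section 9.1 no formal testing. No adjusted estimate is described.

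**The concern.** A characteristic that eligibility holds constant cannot explain differences between participants, so one named example cannot be analysed as written. The lists and the criterion disagree. Because the synopsis omits primiparity, a reader cannot be sure which of them is out of date.

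The lists also leave out a baseline variable that the design allows to vary and that the protocol treats as relevant to its target behaviour. PWR is measured at a fixed time after baseline, and therefore at different times after delivery, yet it is judged against a single 5 kg benchmark. At stake is some precision in the weight estimates that will feed the larger trial, and how well a chance difference between two arms of 20 in postpartum stage can be accounted for.

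**Working it through.** **1. The plan's own figure.** Section 9.2 gives 95% interval widths of 0.31 (n = 40) and 0.44 (n = 20). The Wald width at p = 0.5 is 2 × 1.96 × √(0.25/n), which gives 0.310 and 0.438. Both reproduce, and nothing below depends on them.

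**2. Parity.** With all 40 participants primiparous, the variance of parity is 0. A design matrix of intercept plus parity has rank 1, so no parity effect can be estimated.

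**3. Spread of time since delivery.**
- Entry at the outer limits: (6 + 1) − (3 − 1) = 5 months. At the nominal limits: 6 − 3 = 3 months.
- Final visit: Day 112 (Section 1.3) is 112/30.44 = 3.7 months after the start, so outer-limit entry of 2 to 7 months becomes about 5.7 to 10.7 months postpartum when PWR is measured.

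**4. Chance imbalance between arms of 20.** Assume entry is uniform over the window (not stated in the documents). Then SD = width/√12, SE of the difference in means = SD × √(2/20), and the 95% chance range is ±1.96 × SE.

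| Window | SD (months) | SE (months) | 95% range (months) |
|---|---|---|---|
| 5 months | 1.44 | 0.456 | ±0.9 |
| 3 months | 0.87 | 0.274 | ±0.5 |

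**5. Effect of adjustment on interval width, one covariate.** Let r be the within-arm correlation of the covariate with the outcome. The documents give none, so a range is shown. Ignoring the cost of estimating the slope, the interval narrows by 1 − √(1 − r²). Allowing for that cost, with a normally distributed covariate and 20 measured per arm, the expected variance is multiplied by 1 + 1/36. The t quantile rises from 2.0244 (38 df) to 2.0262 (37 df). The width ratio is then √[(1 − r²) × 37/36] × 2.0262/2.0244.

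| r | Cost ignored | Width ratio | Net change in width |
|---|---|---|---|
| 0.1 | 0.5% narrower | 1.010 | about 1% wider |
| 0.2 | 2.0% narrower | 0.994 | under 1% narrower |
| 0.3 | 4.6% narrower | 0.968 | about 3% narrower |
| 0.5 | 13.4% narrower | 0.879 | about 12% narrower |

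Break-even: r² = 1 − (36/37) × (2.0244/2.0262)² = 0.029, so r ≈ 0.17.

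**6. Two covariates.** With baseline weight added, the variance multiplier becomes 1 + 2/35 and the t quantile 2.0281 (36 df). Break-even is at a joint (multiple) correlation of √[1 − (35/37) × (2.0244/2.0281)²] ≈ 0.24. At joint correlations of 0.3 and 0.5 the interval is about 2% and 11% narrower.

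**The case against.** **The list is only illustrative.** This stands. Time since delivery is not excluded, merely not named in advance, and the analysis is exploratory. It does not rescue parity, which is one of the examples chosen and cannot be analysed.

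**Naming a covariate narrows no interval.** This also stands. Section 9.4.2 describes an exploration of covariates, not an adjustment model. Any gain comes from fitting an adjusted estimate, which is a small addition to a descriptive plan and more than a wording change.

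**Infant sleep is already measured.** True: Section 8.1 includes an infant sleep questionnaire, given at baseline and the final visit. That covers one route by which postpartum stage may act, but it does not record the stage itself.

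**The gain may be nil.** At correlations below about 0.17 adjustment slightly widens the interval. The relevant correlation is with 16-week weight change, and the documents give no basis for assuming it is large.

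Three stronger readings are tempting and are not supported:
- That omitting time since delivery biases the comparison or lets imbalance pass as effect. Under randomization the unadjusted difference is unbiased, and its interval already reflects chance imbalance.
- That Section 5 says the meaning of retained weight changes within the window. It links retention during the period as a whole to later obesity; only its infant-sleep statement concerns change over time.
- That the variable is already in the data set. Screening must establish that a participant is within the window, but no listed assessment says the delivery date or weeks postpartum is kept.

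**Conclusion.** The point holds as a minor one. It is certain from the documents that parity cannot be analysed in an all-primiparous sample and that Sections 3 and 9.4.2 conflict with Sections 5 and 5.1. It is equally clear that time since delivery is not named, although entry may span 3 months nominally and 5 at the outer limits.

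The benefit of using it is conditional. At an assumed correlation of 0.3 to 0.5 for a single covariate, the interval for the between-arm weight estimate narrows by about 3% to 12% net of cost. These figures assume that all 40 are measured at the end; losses would raise the cost slightly. What is gained is precision and an estimate that takes account of the imbalance actually observed. The feasibility and acceptability analyses and the sample-size justification are unaffected.

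**What to change.** 1. In Sections 3 and 9.4.2, delete parity so that the lists agree with the primiparity criterion, and name weeks since delivery at baseline (continuous) in its place. State primiparity and the unit of the entry window in the synopsis.
2. Record the delivery date at screening, derive weeks since delivery at baseline, and summarize it by arm.
3. In Section 9.4.2, report between-arm estimates of weight change and PWR with 95% confidence intervals, both unadjusted and adjusted for baseline weight and weeks since delivery. Keep them descriptive, with no test.

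**Cost.** One recorded date, one simple linear model per outcome and up to two degrees of freedom. If the covariates turn out to be weakly related to the outcome, the adjusted interval may be slightly wider, which is why the unadjusted estimate stays beside it. There is essentially no added participant burden, and no sample-size figure changes.

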10 SUPPORTING DOCUMENTATION AND OPERATIONAL CONSIDERATIONS

10.1.1 INFORMED CONSENT PROCESS

Informed consent will be obtained during an in-person meeting in the PHB label. Informed consent will be obtained before baseline assessments.

10.1.1.1 CONSENT/ASSENT AND OTHER INFORMATIONAL DOCUMENTS PROVIDED TO PARTICIPANTS

Consent forms describing in detail the study intervention, study procedures, and risks are given to the participant, and written documentation of informed consent is required prior to starting intervention/administering the study intervention.

10.1.1.2 CONSENT PROCEDURES AND DOCUMENTATION

Informed consent is a process that is initiated prior to the individual's agreeing to participate in the study and continues throughout the individual's study participation. Consent forms will be Institutional Review Board (IRB)-approved and the participant will be asked to read and review the document. The investigator will explain the research study to the participant and answer any questions that may arise. A verbal explanation will be provided in terms suited to the participant's comprehension of the purposes, procedures, and potential risks of the study and of their rights as research participants. Participants will have the opportunity to carefully review the written consent form and ask questions prior to signing. The participants should have the opportunity to discuss the study with their family or surrogates or think about it prior to agreeing to participate. The participant will sign the informed consent document prior to any procedures being done specifically for the study. Participants must be informed that participation is voluntary and that they may withdraw from the study at any time without prejudice. A copy of the informed consent document will be given to the participants for their records. The informed consent process will be conducted and documented in the source document (including the date), and the form will be signed before the participant undergoes any study-specific procedures. The rights and welfare of the participants will be protected by emphasizing to them that the quality of their medical care will not be adversely affected if they decline to participate in this study.

10.1.2 CONFIDENTIALITY AND PRIVACY

Participant confidentiality and privacy is strictly held in trust by the participating investigators, their staff, and the sponsor(s) and their interventions. This confidentiality is extended to cover baseline and post-intervention assessments. Therefore, the study protocol, documentation, data, and all other information generated will be held in strict confidence. No information concerning the study or the data will be released to any unauthorized third party without the prior written approval of the sponsor.

All research activities will be conducted in as private a setting as possible.

The study monitor, other authorized representatives of the sponsor, and representatives of the Institutional Review Board (IRB) may inspect all documents and records required to be maintained by the investigator.

The study participant's contact information will be securely stored on REDCap for internal use during the study. At the end of the study, all records will continue to be kept in on REDCap for as long a period as dictated by the reviewing IRB, Institutional policies, or sponsor requirements.

Study participant research data, which is for purposes of statistical analysis and scientific reporting, will be stored on REDCap. This will not include the participant's contact or identifying information. Rather, individual participants and their research data will be identified by a unique study identification number. The study data entry and study management systems used by research staff will be secured and password protected.

10.1.2.1 DATA COLLECTION AND MANAGEMENT RESPONSIBILITIES

1. Data Collection Responsibilities

- a. Study Personnel: The research assistant or project coordinator will be involved in data collection under the supervision of the principal investigator.
- b. Training: The principal investigator will ensure all study personnel involved in data collection receive appropriate training on the study protocol, data collection instruments, data entry procedures, and ethical considerations (e.g., informed consent, confidentiality).
- c. Data Collection Instruments: Data collection will include physical measurements (i.e., measured height and weight), surveys and questionnaires, and semi-structured interviews. We selected previously validated interviewer-administered questionnaires relevant to the study objectives.
- d. Data Collection Procedures: Study data will be collected before randomization and post-intervention by a study team member. The study team member will provide participants a QR code or HTML link to the self-reported surveys, which can be completed on the study computer or the participant's mobile device, at their preference.
- e. Quality Control: Implement quality control measures to ensure the accuracy, completeness, and consistency of data collection, such as periodic checks, data audits, or inter-rater reliability assessments.

2. Data Management Responsibilities

- a. Data Entry: The project coordinator developed the REDCap database that will be used for data entry. Describe the procedures for entering data into the study database, including any software or platforms used, data entry formats, and procedures for verifying the accuracy of data entry.
- b. Data Storage: Study data will be stored on REDCap, an encrypted, secure server maintained by the University of Pittsburgh. Hard copies, if any, will be stored in a locked filing cabinet located in the PI's university office, accessible only by authorized study team members.
- c. Data Access: Only study team members will have full access to the study data. We will adhere to NIH's policy on dissemination of NIH-funded clinical trial information by taking the following steps:
 - i. Registering the trial with ClinicalTrials.gov within 21 calendar days of enrollment of the first participant

- ii. Submitting trial results to ClinicalTrials.gov no later than one year following the completion date of the study
 - iii. Include a statement in our informed consent document that explains that this clinical trial is registered with ClinicalTrials.gov and that the results of the study (not including any identifying information) will be reported in accordance with the NIH dissemination policy for clinical trials
 - iv. Working with the University of Pittsburgh's Office for ClinicalTrials.gov to ensure that all requirements within the policy are adhered to in a timely fashion
 - v. Create a newsletter to share findings with our study participants
 - vi. Submit abstracts to national scientific conferences and submit manuscripts for publication
 - vii. Will make de-identifiable study data available to researchers upon request after primary outcome manuscripts are published.
- d. Data Monitoring: The PI will review data quality bi-monthly and ensure that there are no unexpected trends or safety issues.
 - e. Data Cleaning and Validation: Data will undergo range checks for each variable, logical consistency checks, and manual outlier detection. Discrepancies will be resolved by referring back to the original data source.
 - f. Data Analysis: See section 9.4 for details on the statistical analysis plan.
 - g. Data Retention and Destruction: Study data will be retained for a period of 7 years post-study completion, as per institutional guidelines. Following this period, hard copies will be shredded.

